10.0 SAFETY ANALYSES

The safety analysis will be performed using the Safety Population. The safety parameters will include adverse events (AEs) and vital signs. For each safety parameter of the vital signs, the last nonmissing safety assessment before the first dose of study intervention will be used as the baseline for all analyses of that parameter. Continuous variables will be summarized by number of participants and mean, SD, median, minimum, and maximum values. Categorical variables will be summarized by number and percentage of participants.

10.1 ADVERSE EVENTS

Adverse events will be coded by SOC and PT using the MedDRA, version 22.0 or newer.

An AE will be considered a treatment-emergent adverse event (TEAE) if the AE began or worsened (increased in severity or became serious) on or after the date of the first dose of study intervention.

An overall summary of AEs by study intervention group will be provided.

The number and percentage of participants reporting TEAEs will be summarized by study intervention group using MedDRA PT nested within SOC. Events will be in alphabetic order of SOC and by descending frequency of PTs within each SOC.

The total number of TEAEs by severity will be summarized by study intervention group.

Treatment-related TEAEs will be tabulated by descending frequency of PTs within the SOC. If more than 1 AE is coded to the same PT for the same patient, the patient will be counted only once for that PT using the greatest severity and strictest causality for the summarization by severity and causal relationship.

The number and percentage of participants who have treatment emergent serious adverse events (TESAEs) will be summarized by SOC, PT, and study intervention group if 5 or more participants reported such events.

The number and percentage of participants in the Safety Population who have TEAEs leading to premature discontinuation of the study intervention will be summarized by SOC, PT, and study intervention group if 5 or more participants reported such events.

To assess possible distant spread of toxin (PDSOT), MedDRA preferred terms that may be associated with botulinum toxin effects have been identified and are shown in Table 10-1. All AEs associated with PDSOT will be tabulated by PT and study intervention group; in addition, all PDSOT AEs will be listed by subject.

Cardiac Disorders	Nervous System Disorders	
Bradycardia	Bulbar palsy	
	Cranial nerve palsies multiple	
Eye Disorders	Cranial nerve paralysis	
Accommodation disorder	Dysarthria	
Diplopia	Facial paralysis	
Extraocular muscles paresis	Facial paresis	
Eyelid function disorder	Hyporeflexia	
Eyelid ptosis	Hypotonia	
Pupillary reflex impaired	Paralysis	
Vision blurred	Paresis cranial nerve	
	Peripheral nerve palsy	
Gastrointestinal Disorders	Peripheral paralysis	
Constipation	Speech disorder	
Dry mouth	Vocal cord paralysis	
Dysphagia	Vocal cord paresis	
Ileus paralytic		
	Renal and Urinary Disorders	
Infections and Infestations	Urinary retention	
Botulism		
	Respiratory, Thoracic and Mediastinal Disorders	
Musculoskeletal and Connective Tissue Disorders	Aspiration	
Muscular weakness	Diaphragmatic paralysis	
	Dysphonia	
	Dyspnoea	
	Pneumonia aspiration	
	Respiratory arrest	
	Respiratory depression	
	Respiratory failure	
	Reproductive System and Breast Disorders	
	Pelvic floor muscle weakness	

Table 10-1MedDRA System Organ Class and Preferred Terms Evaluated for Possible Distand
Spread of Toxin

Note: Table is based on MedDRA 22.0; the actual list used for analysis will be based on the MedDRA version in use at the time of database lock.

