4.1. Overall Design

This is a 6-month, multicenter study consisting of a single treatment period and approximately 150 enrolled participants. The study is a double-blind, randomized, placebo-controlled, single-study-intervention design, which will assess the safety and efficacy of BOTOX treatment for MMP (see Schema, Section 1.2).

On Day 1, participants will be randomized in a 1:1:1 ratio to receive a single treatment of BOTOX 48 U, BOTOX 72 U, or placebo. Randomization will be stratified at each investigator site by the participant's baseline MMPS Grade (4 or 5). Up to 8 scheduled visits are planned: screening (Day -14 to Day -1), baseline (Day 1), follow-up (Days 30, 60, 90, 120, 150), and study exit (Day 180).

After verification that the participants meet all inclusion and exclusion criteria and completion of all baseline study procedures, participants will be randomized and enrolled. Once enrolled, participants will spend approximately 6 months in the study.

On Day 1, participants will receive a single treatment of either BOTOX (48 U or 72 U) or placebo administered bilaterally to the masseter muscles as 3 injections/masseter in the area of maximal muscle bulge (Figure 6-1, Section 6.1). The final reconstituted volume for all interventions will be the same 1.8 mL (0.3 mL per injection site). This is to ensure the investigator and participant remain blinded to the study intervention administered. An IDR, who has no other participant-related activities for this study, will prepare all study interventions. After study intervention is administered on Day 1, participants will return for follow-up assessments

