6.7. Intervention After the End of the Study

No interventions after the end of the study are planned.

7. Discontinuation of Study Intervention and Participant Discontinuation/Withdrawal

Participants may voluntarily withdraw from the study at any time. A premature discontinuation will occur if a participant who signs the ICF and is dosed ceases participation in the study, regardless of circumstances, before the completion of the protocol-defined study procedures.

Notification of early participant discontinuation from the study and the reason for discontinuation will be made to the sponsor and will be clearly documented on the appropriate eCRF.

Reasons for discontinuation from the study intervention and/or the study may include the following commonly used or other acceptable terms:

| Commonly Used Terms | Other Acceptable Terms | | | | |
|-----------------------------|------------------------|--|--|--|--|
| Adverse event | Death | | | | |
| Lack of efficacy | | | | | |
| Lost to follow-up | | | | | |
| Other | | | | | |
| Physician decision | | | | | |
| Pregnancy | | | | | |
| Protocol deviation | | | | | |
| Site terminated by sponsor | | | | | |
| Study terminated by sponsor | | | | | |
| Withdrawal by participant | | | | | |

If a pregnancy is confirmed after the participant has received study intervention, the participant may choose to exit the study after appropriate safety follow-up or to remain in the study for all safety and efficacy follow-up assessments through the end-of-study visit.

Definitions of the standard terms are provided in Appendix 4.

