7.1. Discontinuation of Study Intervention

Not applicable, as participants receive only a single treatment with study intervention on Day 1.

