9.4.2.1. Adverse Events

An AE will be considered a TEAE if:

• The AE began on or after the date of the first dose of study intervention; or

• The AE was present before the date of the first dose of study intervention, but increased in severity or became serious on or after the date of the first dose of study intervention.

An AE will be considered a TESAE if it is a TEAE that additionally meets any SAE criteria.

The number and percentage of participants reporting TEAEs in each study intervention group will be tabulated by system organ class and preferred term and by system organ class, preferred term, and severity.

The number and percentage of participants reporting treatment-related TEAEs in each study intervention group will be tabulated by system organ class and preferred term.

If more than 1 AE is coded to the same preferred term for the same participant, the participant will be counted only once for that preferred term using the most severe and most related occurrence for the summarizations by severity and by relationship to study intervention.

Summary tables will be provided for participants with SAEs and participants with AEs leading to discontinuation if 5 or more participants reported such events. Listings of all AEs, SAEs, and AEs leading to discontinuation by participant will be presented.

The definitions of an AE and SAE can be found in Appendix 2.

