7.0 PATIENT DISPOSITION

Participant disposition encompasses the distribution of participants screened, randomized, treated, and who completed or discontinued the study (along with reasons for withdrawal/discontinuation). Participant disposition will be summarized for all screened participants in total and by study intervention group.

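### SAP 10.1 ties its discontinuation table to stopping the study intervention, which almost no one can do after a single treatment, so the SOC/PT breakdown of AEs behind study exits would not be produced

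*SAP*

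**What the plan says.** SAP 10.1 defines the table this way: "TEAEs leading to premature discontinuation of the study intervention will be summarized by SOC, PT, and study intervention group if 5 or more participants" report such events. The condition, "TEAEs leading to premature discontinuation of the study intervention", is attached to the intervention, not to the study.

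Protocol 7.1 deals with discontinuation of the study intervention in one sentence: "Not applicable, as participants receive only a single treatment with study intervention on Day 1". Withdrawal from the study is handled separately, in Protocol 7.2.

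Protocol 9.4.2.1 sets the same threshold without the restriction. It promises summary tables for "participants with AEs leading to discontinuation if 5 or more participants reported such events". It then adds, with no threshold: "Listings of all AEs, SAEs, and AEs leading to discontinuation by participant will be presented".

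SAP 7.0 separately summarises, in total and by study intervention group, participants "who completed or discontinued the study (along with reasons for withdrawal/discontinuation".

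**The concern.** The SAP presents itself as a more detailed elaboration of the protocol's analyses. Here it adds a qualifier that the protocol's statistical section does not have, and the qualifier names something the protocol says does not occur in this design. The SAP text neither announces nor explains the narrowing.

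Comparing the safety of BOTOX with placebo is a primary objective, and AE incidence is one of its endpoints. Protocol 4.2 explains that AE analysis was the most sensitive safety assessment in the preceding Phase 2 study, which is why this trial relies on routine AE and vital-sign monitoring. A by-arm table of the events that led participants to leave is an ordinary part of that comparison. A programmer who applies the SAP wording as it stands would not produce it.

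**Working it through.** The plan states no figure to reproduce here, so the check is mainly a comparison of texts. A short calculation then shows how often the table would matter.

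**Step 1. Who can meet the SAP condition?** Treatment is a single session on Day 1, "administered bilaterally to the masseter muscles as 3 injections/masseter in the area of maximal muscle bulge", so 3 × 2 = 6 injections. Once the session is complete there is nothing left to discontinue. The only conceivable case is an AE that stops the session before the sixth injection. The condition is therefore essentially, though not strictly, unattainable.

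**Step 2. What does the protocol mean by the same table?**

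| Place | Discontinuation of what | Threshold |
|---|---|---|
| SAP 10.1 table | Study intervention | 5 or more participants |
| Protocol 7.1 | Study intervention: not applicable | – |
| Protocol 9.4.2.1 table | Not restricted | 5 or more participants |
| Protocol 9.4.2.1 listing | Not restricted | None |
| SAP 7.0 disposition | Study, with reasons | None |

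Protocol Section 7 describes premature discontinuation as a dosed participant ceasing to take part in the study before its procedures are complete. With intervention discontinuation ruled out by 7.1, the protocol's unrestricted term can in practice only mean leaving the study.

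**Step 3. What is lost and what remains?** Under the SAP wording the count stays at or near 0, the threshold of 5 is not realistically reached, and the table is omitted. This holds whatever the number of AE-driven study exits. What remains is the disposition count by reason and group (Adverse event is one of the reasons named in Protocol Section 7) and the protocol's listing by participant. The missing piece is the breakdown by SOC, PT and group.

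**Step 4. How often would the corrected table appear?** Inputs: N = 150 (planned total) and a threshold of 5, taken as applying to all groups pooled. The documents give no AE-exit rate p, so a range is assumed, equal across arms and independent between participants. The formula is P(X ≥ 5) = 1 − Σ from k = 0 to 4 of C(150, k) p^k (1 − p)^(150 − k).

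| Assumed p | Expected exits, 150 × p | P(X ≥ 5) |
|---|---|---|
| 0.5% | 0.75 | 0.1% |
| 1% | 1.5 | 1.8% |
| 2% | 3.0 | 18.3% |
| 3% | 4.5 | 46.9% |
| 5% | 7.5 | 87.4% |

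With corrected wording the table is unlikely if AE exits are rare and likely if they reach about 5%. With the present wording it is essentially never produced at any of these rates.

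**The case against.** The strongest reply is that nothing important is hidden. A reader might infer from SAP 10.1 that AE-driven exits are never summarised, or that the plan would report none whatever happened. The documents do not support that: SAP 7.0 gives the by-arm count with no threshold, and Protocol 9.4.2.1 gives the listing. SAP 10.1 also promises an overall AE summary whose rows it does not specify, and SAP 4.0 places table and listing specifications in a separate document that is not available here. A discontinuation row there cannot be ruled out. All of this stands, and it confines the point to the SOC/PT table.

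A reader might also call the count zero by definition. That is slightly too strong, because a session of six injections can be interrupted. And below 5 participants the table is omitted, not printed empty.

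Nor does the 10% dropout assumption (10% of 150 = 15 participants) measure the loss. It covers exits for all causes and says nothing about how many are due to AEs.

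Finally, the phrase may be template language. The protocol is loose too: Section 7 gives one list under the words "Reasons for discontinuation from the study intervention and/or the study may include the following commonly used or other acceptable terms", and Sections 8 and 8.3 speak of discontinuing the intervention despite 7.1. A sensible programmer might read the SAP phrase as study exit. That is plausible, but the protocol also treats the two kinds of discontinuation in separate sections, so the equivalence cannot be taken for granted. An analysis plan should not depend on the programmer guessing against its wording.

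**Conclusion.** The SAP wording is wrong for this design, and its impact is small. It conflicts with Protocol 7.1 and is narrower than Protocol 9.4.2.1. Read literally, it means that the summary table the protocol planned, which the SAP lays out by SOC, PT and group, would not be produced even with 5 or more AE-driven study exits.

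The conclusion rests on a literal reading of SAP 10.1 and on the table specifications not correcting it elsewhere. How likely the loss is depends on an AE-exit rate that the documents do not give. AE collection, the main TEAE tables, the sample size and all efficacy analyses are untouched.

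**What to change.** In SAP 10.1, change the condition to TEAEs leading to premature discontinuation from the study, keeping the layout and the threshold of 5 that both documents share. In the same paragraph, state the by-participant listing of AEs leading to discontinuation already promised in Protocol 9.4.2.1, and bring the table and listing specifications into line.

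The cost is one line of SAP text and a programming flag. The protocol already requires the reason for discontinuation to be documented on the eCRF, so no new data are needed. Showing the by-arm count in the overall AE summary whatever the total would be convenient, but it is a preference, since the disposition summary already gives that count.

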10.2 VITAL SIGNS

Allergan

BOTOX

Descriptive statistics (mean, SD, median, Q1, Q3, minimum, and maximum) for vital signs (systolic and diastolic blood pressures, respiratory rate, and pulse rate) and changes from baseline values at each visit and at the end of study will be presented by study intervention group.

Vital sign values will be considered PCS if they meet both the observed-value criteria and the change-from-baseline criteria listed in Table 10-2. A listing of patients with PCS postbaseline values will be provided, including the PID number, baseline and all postbaseline (including non-PCS) values.

D	Flag	Criteria ^a		
Parameter		Observed Value	Change From Baseline	
Sitting systolic blood	High	> 140	Increase of ≥ 20	
pressure, mm Hg	Low	< 90	Decrease of ≥ 20	
Sitting diastolic blood	High	> 90	Increase of ≥ 15	
pressure, mm Hg	Low	≤ 50	Decrease of ≥ 15	
Sitting and a rota have	High	> 100	Increase of ≥ 15	
Sitting pulse rate, opm	Low	≤ 50	Decrease of ≥ 15	

 Table 10-2
 Criteria for Potentially Clinically Significant Vital Signs

a A postbaseline value is considered potentially clinically significant if it meets both the observed-value and the change-from-baseline criteria.

bpm = beats per minute.

11.0 INTERIM ANALYSIS

No interim analyses are planned for this study.

12.0 DETERMINATION OF SAMPLE SIZE

The primary efficacy parameter is proportion of responders who achieve MMPS Grade \leq 3 at Day 90 (last observation carried forward). Based on previous data from study 191622-130 and the assumption of \geq 34% difference in MMPS response rate between BOTOX 48 U or 72 U and placebo and 10% dropout rate, approximately 50 participants will provide > 90% power using a 2-sided Mantel-Haenszel test at 5% significance level.

13.0 STATISTICAL SOFTWARE

Statistical analyses will be performed using SAS version 9.4 (or newer) on a Linux operating system.

14.0 DATA HANDLING CONVENTIONS

14.1 VISIT TIME WINDOWS

Table 14-1 presents the visits assigned for efficacy and safety analyses and the corresponding range of study intervention days (window) during which an actual visit may occur.

Derived Visit	Scheduled Visit Day ^a	Window	
Baseline	Day 1	$Days \le 1$	
Day 30	Day 30	Days [2, 45]	
Day 60	Day 60	Days [46, 75]	
Day 90	Day 90	Days [76, 105]	
Day 120 Day 120		Days [106, 135]	
Day 150	Day 150	Days [136, 165]	
Day 180	Day 180	$Days \ge 166$	
End of Study ^b	Final or Termination Visit during the double-blind treatment period		

Table 14-1Visit Time Windows

a Relative to the date of the first dose of study intervention. Day 1 = the date of the first dose of study intervention. There is no Day 0.

b Presented in analysis tables for safety parameters, including but not limited to vital signs.

If the assessment date is on or after the date of the first dose of study intervention, the study day is calculated by assessment date – date of the first dose of study intervention + 1. If the assessment date is before the date of the first dose of study intervention, the study day is calculated by assessment date – date of the first dose of study intervention. Therefore, a negative day indicates a day before the start of the study intervention. If the assessment date is unavailable, use the visit date instead.

If a participant has 2 or more visits within the same window, the last visit with a nonmissing value will be used for analysis.

14.2 DERIVED VARIABLES

Not applicable.

14.3 REPEATED OR UNSCHEDULED ASSESSMENTS OF SAFETY PARAMETERS

If a participant has repeated assessments before the start of the first study intervention, the results from the final nonmissing assessment made prior to the start of the study intervention will be used as baseline. If end-of-study assessments are repeated or if unscheduled visits occur, the last nonmissing postbaseline assessment will be used as the end-of-study assessment for generating summary statistics.

14.4 MISSING SEVERITY ASSESSMENT FOR ADVERSE EVENTS

If severity is missing for an AE that started before the date of the first dose of study intervention, an intensity of mild will be assigned. If severity is missing for an AE that started on or after the date of the first dose of study intervention (based on date, and time if known), an intensity of severe will be assigned. The imputed values for severity assessment will be used for the incidence summary; the values will be shown as missing in the data listings.

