8.3. Adverse Events and Serious Adverse Events

The definitions of an AE or SAE can be found in Appendix 2.

AEs will be reported by the participant (or, when appropriate, by a caregiver, surrogate, or the participant's legally authorized representative).

The investigator and any qualified designees are responsible for detecting, documenting, and recording events that meet the definition of an AE or SAE and any other study-specific terms as relevant and remain responsible for following up AEs that are serious, considered related to the study intervention or study procedures, or that caused the participant to discontinue the study intervention or study (see Section 7).

8.3.1. Time Period and Frequency for Collecting Adverse Event and Serious Adverse Event Information

All AE/SAEs from the signing of the ICF will be collected at the timepoints specified in the SoA and as observed or reported spontaneously by study participants.

Medical occurrences that begin before the start of study intervention, but after obtaining informed consent will be recorded in the AE section of the eCRF and will be considered pretreatment AEs.

All SAEs will be recorded and reported to the sponsor or designee within 24 hours, as indicated in Appendix 2. The investigator will submit any updated SAE data to the sponsor within 24 hours of it being available.

Investigators are not obligated to actively seek AE or SAE information after conclusion of the study participation. However, if the investigator learns of any SAE, including a death, at any time after a participant has been discharged from the study, and he/she considers the event to be

reasonably related to the study intervention or study participation, the investigator must promptly notify the sponsor.

The method of recording, evaluating, and assessing causality of AEs and SAEs and the procedures for completing and transmitting SAE reports are provided in Appendix 2.

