14.5 MISSING CAUSAL RELATIONSHIP TO STUDY INTERVENTION FOR ADVERSE EVENTS

If the causal relationship to study intervention is missing for an AE that started before first dose of study intervention, a causality of no will be assigned. If the causal relationship to the study intervention (per the investigator) is missing for an AE that started on or after the date of the first dose of study intervention (based on date, and time if known), a causality of yes will be assigned. The imputed values for causal relationship to study intervention will be used for the incidence summary; the values will be shown as missing in the data listings.

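### SAP 14.4 and 14.5 impute missing AE severity and causality by start date alone, so a pre-dose AE that becomes treatment-emergent by worsening is filled in as mild and unrelated

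*SAP*

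**What the plan says.** SAP 14.4 provides that where "severity is missing for an AE that started before the date of the first dose of study intervention, an intensity of mild will be assigned". For an AE that started on or after that date, "an intensity of severe will be assigned". SAP 14.5 has the same structure for causality: where the relationship "is missing for an AE that started before first dose of study intervention, a causality of no will be assigned"; for later onsets, "a causality of yes will be assigned". Both sections send the imputed value to the incidence summary and leave the field blank in the listings.

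The definition of a TEAE is wider than onset after dosing. Under SAP 10.1 an AE is treatment-emergent "if the AE began or worsened (increased in severity or became serious) on or after the date of the first dose of study intervention". Protocol 9.4.2.1 sets out the second limb separately, for a change from the day of dosing onward: "The AE was present before the date of the first dose of study intervention, but increased in severity or became serious".

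Protocol 8.3.1 confirms that such events are captured. Occurrences between consent and dosing "will be recorded in the AE section of the eCRF and will be considered pretreatment AEs".

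**The concern.** The definition has two routes to treatment-emergent status, and the imputation rules recognise only one. A TEAE that arrives by the worsening route receives the least cautious value for a missing field, while a TEAE that arrives by new onset receives the most cautious one.

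This runs against the plan's own approach elsewhere. When a participant has several AEs under one preferred term, SAP 10.1 keeps the greatest severity and the strictest causality.

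At stake are the severity and relatedness breakdowns of the TEAE tables. They support the safety comparison that Protocol Section 3 places under the primary objectives.

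**Working it through.** The plan states no figure to reproduce. The check crosses the TEAE definition (SAP 10.1, Protocol 9.4.2.1) with the two imputation rules (SAP 14.4, 14.5).

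| AE type | TEAE? | Missing severity becomes | Missing causality becomes |
|---|---|---|---|
| (a) starts on or after first dose | Yes | severe | yes |
| (b) starts before first dose, no worsening | No | mild | no |
| (c) starts before first dose, then increases in severity or becomes serious | Yes | mild | no |

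**Where the values go.** SAP 10.1 summarises TEAEs by severity and tabulates treatment-related TEAEs. Type (b) is not a TEAE and does not enter those tables. The pre-dose values can therefore alter them only through type (c), the class for which they are not cautious.

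**Causality.** A type (c) event with a blank relationship is set to no and drops out of the treatment-related table. This applies whether the event qualified by increased severity or by becoming serious.

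**Severity.** This half is narrower. An event that qualifies by increased severity normally has the higher grade on record, so nothing is imputed. The rule mainly reaches an event that became serious with its severity blank. Protocol Appendix 2 separates serious from severe, so that combination is possible, and the event would appear as mild in the severity summary.

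**Start date.** The trace needs the pre-dose start date to be kept. Protocol 8.3.3 points that way, since follow-up information goes into the eCRF that was first completed. Appendix 2, however, lists exacerbation of a pre-existing chronic or intermittent condition as meeting the AE definition. That could lead a site to open a new record. Neither document settles it.

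**Size.** The documents give no rate of missing severity or causality and no count of worsened pre-dose AEs, so the number affected cannot be calculated; its minimum is 0. As a scale only, 1 participant / 50 per arm = 0.02, or 2 percentage points.

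**The case against.** The strongest reply is that the conditions rarely coincide. Onset must fall between consent and dosing, with screening running from Day -14 to Day -1. The event must then worsen, a required field must be blank, and the worsening must not have its own record. Protocol Appendix 2 obliges the investigator to assess causality for each occurrence of every AE, and before an SAE is first transmitted. Source data verification is a further check. The listings show the value as missing, so each case can be found. Another recorded occurrence of the same preferred term in the same participant would override an imputed mild or no. All of this stands, and it limits the size of the problem. It does not remove the mismatch between the rules.

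The mild rule also has a possible rationale: if the missing item is the pre-dose grade, assuming mild makes a later increase easier to detect. SAP 14.4 does not limit the rule to that use, and the argument gives no support for setting causality to no.

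Three stronger readings are tempting and should not be drawn.

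- A reader might infer that imputing mild makes the event fail the worsening test, so that it leaves the TEAE tables and lowers overall TEAE incidence. The SAP does not say that imputed severity sets the TEAE flag. Where it wants an imputed value to decide TEAE status, as for partial dates in SAP 14.6, it says so.
- A reader might suppose that causality is especially likely to be blank for these records because no treatment had been given at first entry. Neither document supports this, and Appendix 2 points the other way.
- A reader might set the effect against the earlier Phase 2 study's rates of treatment-related mastication disorder (5.3%) or facial paresis (2.7%). The protocol describes those as local effects following injection, whereas the affected class must begin before it.

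**Conclusion.** The concern holds in a limited form. As written, SAP 14.4 and 14.5 assign mild and no to a defined class of TEAEs, against the severe and yes given to all other TEAEs with the same missing field. The causality half is the firmer: the event leaves the treatment-related TEAE table. The severity half mainly concerns AEs that became serious.

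The conclusion assumes that a worsened AE keeps its original start date, which Protocol 8.3.3 suggests but does not settle. Only the severity and relatedness breakdowns can be shown to move. The number of events is probably very small and may be zero, and no effect on a trial conclusion has been shown. The correction is still worth making, because the inconsistency is plain and choosing imputation rules after unblinding would invite criticism.

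**What to change.** Before database lock, amend SAP 14.4 and 14.5 in one of two ways.

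1. Set the TEAE flag first, from recorded data, and key both imputations to it. Any TEAE, by either route, is assigned severe if severity is missing and yes if causality is missing. Only AEs that are not treatment-emergent are assigned mild or no.
2. Alternatively, state that a worsening on or after first dose is entered as a new AE record with its own start date. The existing start-date rule then gives the cautious values without further change.

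The first option needs about two sentences of SAP text and one programming condition. The second needs a recording convention that sites have followed consistently. The downside is that counts of severe and related TEAEs may rise slightly, and assigning those values to a pre-existing condition is a deliberate choice in favour of caution. Types (a) and (b) in the table above would not change under either option.
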